8.3. Statistical Analysis

8.3.1. Subject Disposition, Demography and Baseline Tumor Characteristics

The disposition of subjects will be summarized presenting the number of subjects enrolled, the number and percentage of subjects in each analysis set, the number for whom the study drug was discontinued with the reasons for discontinuation, and the number of subjects who discontinued participation in the study.

Demographic and baseline tumor characteristics will be presented based on the Safety Analysis Set. Baseline demographic and background data, including, but not limited to age, gender, weight, height, BMI, race, ethnicity, GDF-15 serum levels, and ECOG performance status will be listed and summarized using appropriate descriptive statistics.

Baseline tumor characteristics including primary diagnosis, primary tumor location and disease status at baseline will also be summarized. Medical history data will be summarized using frequency tabulations by MedDRA system organ class and preferred term.

8.3.2. Safety Analysis

Summary statistics (mean, median, standard deviation, and range, as appropriate) will be presented descriptively for the following safety endpoints by dose level and overall in Part A and by cohort and overall in Part B. All safety summaries will be presented by dose level (Part A) or cohort (Part B) and visit. The number of subjects experiencing each AE will be summarized by the MedDRA system organ class, MedDRA preferred term, NCI-CTCAE grade, and relationship to study treatment. Serious AEs and irAEs will be summarized separately.

AE summaries:

- Adverse Events - the number of AEs, the proportion of subjects having at least one AE and AEs by MedDRA coded terms will be presented.
- Serious Adverse Events - the number of SAEs, the proportion of subjects having at least one SAE and SAEs by coded terms will be presented.
- Related Adverse Events - the number of related AEs, the proportion of subjects having at least one related AE and related AEs by coded terms will be presented.
- Adverse Events leading to Discontinuation - the number of AEs leading to discontinuation, the proportion of subjects having at least one AE and AEs by coded terms will be presented.

Note: Only treatment-emergent AEs (commencing after exposure to study medication) will be included in the AE summaries. Non-treatment emergent events (starting prior to exposure to study medication) will be included in the subject listings and not included in the above summaries.

Adverse Event Listings:

- Adverse Events, SAEs, DLTs, and AEs leading to discontinuation will also be listed separately
- Details of any deaths will be listed for all subjects
- Any AEs in the study that occur after a subject has received further therapy for cancer (following discontinuation of CTL-002/the defined checkpoint inhibitor) will be flagged in the data listings

Laboratory Evaluations

Clinical laboratory results (including clinical chemistry, hematology, cytokines & chemokines, pharmacodynamic biomarkers, ADA, and urinalysis) will be summarized descriptively by dose level (Part A) or cohort (Part B) and visit, which will also include a display of change from baseline. Listings of abnormal clinical laboratory data according to NCI-CTCAE severity grades (if applicable), abnormal flags (low or high), and clinical significance of the latter will be provided. Shift tables will also be provided tabulating baseline versus on treatment changes in laboratory results.

Vital Signs

Descriptive statistics for vital signs, including weight and BMI, both observed values and changes from baseline, will be summarized by dose level (Part A) or cohort (Part B) and visit. Vital sign measurements will be listed by subject and by visit.

Physical Examination

Abnormal physical examination results will be listed separately.

Electrocardiography

Electrocardiogram parameters and changes from baseline will be summarized by dose level (Part A) or cohort (Part B) and visit using descriptive statistics.

ECOG

ECOG performance status will be summarized by dose level (Part A) or cohort (Part B) and visit using descriptive statistics.

Lumbar Skeletal Muscle Index L3 (L3SMI) (Part A only)

For Part A, The L3SMI results will be summarized by dose level and visit using descriptive statistics.

Mini Cachexia Score (MCASCO) (Part A only)

The 5 MCASCO components and the 3 cachexia classification groups will be summarized by dose level (Part A) and visit using descriptive statistics.

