1.9. Trial Objectives

1.9.1. Primary Objective

Part A (Phase 1; dose escalation):

- To determine the safety and tolerability of IV administration of CTL-002 as monotherapy and in combination with an anti-PD-1 checkpoint inhibitor in subjects with advanced-stage solid tumors that relapsed post or were refractory to a prior anti-PD-1/PD-L1 therapy.

Part B (Phase 2a; expansion):

- To explore the preliminary anti-tumor activity of CTL-002 administered in combination with an anti-PD-1 checkpoint inhibitor in subjects with advanced-stage, relapsed/refractory solid tumors in non-curable state as per current clinical knowledge that have either:
 - (1) bladder cancer, hepatocellular cancer, non-small cell lung cancer, cutaneous squamous-cell carcinoma or melanoma (for melanoma, only cutaneous and mucosal forms, not uveal/ocular) (approved anti-PD-1/PD-L1 indications) that relapsed on or were primary refractory to prior anti-PD-1/PD-L1 therapy with an approved anti-PD-1/PD-L1 compound, or
 - (2) colorectal cancer (micro-satellite stable [MSS]/mismatch-repair competent) and have not received any prior anti-PD-1/PD-L1 therapy, or
 - (3) biomarker cohort with mixed solid tumors (“basket” cohort) that are relapsed on or were primary refractory to prior anti-PD-1/PD-L1 therapy with an approved anti-PD-1/PD-L1 compound.
- To confirm the safety and tolerability of CTL-002 administered as an IV infusion, in combination with an anti-PD-1 checkpoint inhibitor

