1.10.2. Secondary Endpoints

Part A (Phase 1; dose escalation):

- Evaluation of PK parameters of CTL-002 (e.g., C_{max} , AUC, and $t_{1/2}$)
- Evaluation of treatment-emergent cytokine and chemokine profiles in peripheral blood
- Evaluation of treatment-induced anti-drug antibodies (ADA)
- Evaluation of the clinical efficacy according to RECIST V1.1 of CTL-002 as monotherapy and in combination with an anti-PD-1 checkpoint inhibitor by assessment of:
 - The proportion of subjects with tumor shrinkage, a confirmed PR and/or CR, and ORR
 - The interval between the date of first CTL-002 administration and first documented evidence of a PR or CR (TTR)
 - The interval between the date of first documented evidence of PR or CR, until first documented evidence of disease progression or death, due to any cause (DOR)
 - The interval between the date of first CTL-002 administration and the earliest date of disease progression or death (PFS)
 - The interval between the date of first CTL-002 administration and date of death due to any cause (OS)
- To assess appetite, body mass index (BMI), and muscle mass (e.g., L3 skeletal muscle index [L3SMI])

Part B (Phase 2a; expansion):

- Evaluation of PK parameters of CTL-002 (e.g., maximum concentration [C_{max}], area under the curve [AUC], and half-life [$t_{1/2}$])
- Evaluation of treatment-emergent cytokine and chemokine profiles in peripheral blood
- Evaluation of treatment-induced ADA
- Evaluation of GDF-15 serum levels and their correlation with pharmacodynamics and clinical response

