The first subject in the next higher dose cohort will not receive treatment with CTL-002 until the previous dose cohort has met the criteria for dose escalation and agreement from the SRC has been obtained and the decision documented in writing.

Intra-Patient Dose Escalation in Extended Treatment

If any Cohort 1 subjects are still on 0.3 mg/kg treatment when Cohort 2 has been completed and reviewed by the SRC, the subjects can be increased to the Cohort 2 dose of 1.0 mg/kg.

If any Cohort 1 or 2 subjects are still on 1.0 mg/kg treatment when Cohort 3 has been completed and reviewed by the SRC, the subjects can be increased to the Cohort 3 dose of 3.0 mg/kg.

Note: Any subjects still on 0.3 mg/kg treatment must be treated at 1.0 mg/kg prior to advancing to 3.0 mg/kg in agreement with the Sponsor Medical Monitor.

The maximum a subject dose can be increased to, through intra-dose escalation, will be 3.0 mg/kg.

Available safety, PK/pharmacodynamic data, as well as preliminary efficacy data will inform the MTD/dose(s) to be further explored in Part B of the study.

The MTD is defined as the highest dose level of CTL-002 at which no more than 1 out of 6 subjects experienced a DLT during the first 2 treatment cycles (i.e., the first 4 weeks, where CTL-002 is given as monotherapy [Weeks 1 and 2] and in combination with the defined checkpoint inhibitor [Weeks 3 and 4]).

In addition, for Cohorts 3-5, in the absence of any DLT, an additional 3 subjects can be recruited into each of these cohorts (up to a total of 6 subjects per cohort), to increase the understanding of the PK and pharmacodynamic data. This occurs while dose escalation continues. These additional “backfill” subjects will receive the combination treatment of CTL-002 and the defined checkpoint inhibitor once every 2 weeks from Cycle 1 Day 1 onwards, with CTL-002 always administered first and the defined checkpoint inhibitor given thereafter as outlined above.

For Part A subjects (except backfill subjects), 3 sequential tumor biopsies are mandated; one biopsy at baseline, the second biopsy prior to the initiation of the combination therapy (after 2 weeks) and the third after the first cycle of combination therapy (either at the End of Treatment visit or, if combination treatment is continued, at the end of Cycle 2/beginning of Cycle 3).

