6.2.4. Assessment of Safety

The safety and tolerability of IV infusions of CTL-002 monotherapy and CTL-002 in combination with the defined checkpoint inhibitor will be evaluated by the incidence of AEs (all AEs will be evaluated according to NCI-CTCAE v5.0), SAEs, DLTs, and use of concomitant medications. Safety assessments will include: ECGs, physical examinations including neurological examination (motor neuropathy can be conducted by any treating physician, no neurology board certification required), ECOG performance status, vital signs and clinical laboratory samples (hematology, clinical chemistry, coagulation, thyroid function (thyroid stimulating hormone [TSH] and free T3), cytokines, assessment of HbA1c, NT-proBNP, and urinalysis).

Subjects are assessed for safety at Screening, as well as during treatment until the Safety Follow-up Visit. Thereafter safety related to the study is further captured during the follow-up of up to 12 months (Part A)/24 months (Part B) post-treatment. Planned time points for all safety assessments are provided the SoAs in [Table 5](#), [Table 6](#) and [Table 7](#).

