8.1. Statistical Methods

This study is explorative in nature. Thus, no formal statistical comparisons are planned. Descriptive and inferential statistics will be used to summarize the data. Continuous variables will be summarized by number, mean, standard deviation, median, minimum and maximum values. Categorical variables will be summarized by subject counts and related percentages.

Percentages will be calculated using the total subjects per dose group (Part A), and cohort (Part B).

As a general principle, all summaries from Part A, presented by dose group and Part B, presented by cohort, will be displayed separately. No pooling of data from the two parts is planned.

In Part B (Phase 2a; expansion), cohorts with several defined tumor indications will be treated to detect efficacy signals, in a screening effort to identify tumor indications where CTL-002 has clinically relevant antitumor activity. All indications have been selected based upon translational research results by the sponsor and other scientific groups that indicate an immunosuppressive role of GDF-15 in these tumor indications.

To achieve this and based upon a **conditional probability calculation** the following subject numbers are recruited:

- For the **first group**, for bladder cancer, hepatocellular cancer, non-small cell lung cancer, and melanoma, N = 14 response-evaluable subjects will be initially recruited per each tumor indication. This shall allow to detect 2 responses in a cohort with 80% probability if the true response rate is 20% or more, and at least 1 response in the cohort with 77% probability if the true response rate is 10% or more. For cutaneous squamous-cell carcinoma, N = 12 response-evaluable subjects will be recruited initially. This should result in 2 responses or more with 80% probability if the true response rate is 25% or higher
- For the **second group** (colorectal cancer [MSS/mismatch-repair competent, a currently non-approved anti-PD-1/PD-L1 indication]), N = 10 response-evaluable subject will be recruited. This shall allow to detect 1 response with 89% probability (if the true response rate is 20% or more), and 1 response with 80% probability if the true response rate is 15% or more

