8.2. Subject Selection for Analyses

The statistical analysis will be conducted in the following data sets:

- The Safety Analysis Set will consist of all subjects who received at least one dose of CTL-002. Subjects will be analyzed according to the dose level initially received
- The PK Analysis Set will consist of all subjects who received at least one dose of study medication and have at least one measurable concentration of CTL-002
- The Efficacy Evaluable Analysis Set as per statistical definition will consist of all subjects who complete at least 2 cycles of treatment (e.g., 1 cycle monotherapy followed by 1 cycle combination therapy for Part A or 2 cycles combination therapy for Part A backfill and Part B subjects), and have baseline and at least one valid post-baseline tumor assessment demonstrating progression or were declared to be clinically progressing or terminated treatment due to a treatment-related AE

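### The Part A adverse-event summaries fixed in the protocol do not separate monotherapy from combination time, although the primary objective asks for the safety of both

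*Protocol*

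**What the plan says.** The Part A primary objective (Protocol Section 1.9.1) is "To determine the safety and tolerability of IV administration of CTL-002 as monotherapy and in combination with an anti-PD-1 checkpoint inhibitor". Section 6.2.4 repeats both limbs: "The safety and tolerability of IV infusions of CTL-002 monotherapy and CTL-002 in combination with the defined checkpoint inhibitor will be evaluated".

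Under Section 2.2.1.3, escalation subjects receive one CTL-002 dose alone for one two-week cycle and then the combination. Backfill subjects, allowed in Cohorts 3-5 up to a total of six per cohort, "will receive the combination treatment of CTL-002 and the defined checkpoint inhibitor once every 2 weeks from Cycle 1 Day 1 onwards". Section 6.1.3 confirms that they have no monotherapy cycle.

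The analysis text is specific on three points:

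- Layout (Section 8.3.2): "All safety summaries will be presented by dose level (Part A) or cohort (Part B) and visit", with statistics "by dose level and overall in Part A and by cohort and overall in Part B".
- Denominator (Section 8.1): "Percentages will be calculated using the total subjects per dose group (Part A), and cohort (Part B".
- Attribution (Section 8.2, Safety Analysis Set): "Subjects will be analyzed according to the dose level initially received".

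No statement in Section 8 divides adverse events by treatment phase, limits a denominator to subjects who had a monotherapy cycle, or shows backfill subjects apart.

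On efficacy, the Part A secondary endpoint in Section 1.10.2 is "Evaluation of the clinical efficacy according to RECIST V1.1 of CTL-002 as monotherapy and in combination with an anti-PD-1 checkpoint inhibitor". The matching objective in Section 1.9.2 names only the combination.

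**The concern.** An objective with two limbs needs a summary for each. The adverse-event tables count subjects with at least one treatment-emergent event after any study medication. A dose-level row therefore adds together two weeks on CTL-002 alone, all later combination time and, at levels 3-5, subjects who were never on CTL-002 alone. The split by relationship to study treatment does not help, because it is not made by component.

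This matters because a Part B monotherapy cohort is only a possible future amendment (Sections 2.1 and 2.2.2), so within this trial Part A is the only source of single-agent safety data. Section 1.8.5 already cites tolerability in monotherapy as well as in combination when it weighs benefit and risk. The fixed tables would not let a reader check the first half of that statement.

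**Working it through.** **Who has monotherapy exposure**

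Inputs:
- five dose levels with at least 3 escalation subjects each (Sections 2.2.1.3 and 8.5);
- up to 3 backfill subjects in each of Cohorts 3-5 (Section 2.2.1.3);
- Part A minimum of 24 and 25 subjects treated (Sections 8.5 and 1.7.1).

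5 × 3 + 3 × 3 = 15 + 9 = 24, which reproduces the stated minimum. The protocol does not derive its 24 this way, so the 15 + 9 split is an inference from the backfill maximum. On that split, 9/24 = 37.5% of subjects overall, and 3/6 at each of levels 3-5, have no monotherapy time. Levels 1-2 have no backfill, so only time windows are mixed there, not subjects.

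**Effect of the Section 8.1 denominator if it were applied to monotherapy-window events**

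One event at a level with 3 escalation and b backfill subjects, 1/(3 + b):

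| b | Section 8.1 denominator | Exposed only |
|---|---|---|
| 0 | 1/3 = 33% | 33% |
| 1 | 1/4 = 25% | 33% |
| 2 | 1/5 = 20% | 33% |
| 3 | 1/6 = 17% | 33% |

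The exact 95% intervals are 0.8% to 90.6% for 1/3 and 0.4% to 64.1% for 1/6.

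Zero events, two-sided 95% Clopper-Pearson upper limit, 1 − 0.025^(1/n):

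| | Exposed only | Section 8.1 denominator |
|---|---|---|
| One level (3-5), full backfill | 0/3: 70.8% | 0/6: 45.9% |
| Overall, 24 subjects | 0/15: 21.8% | 0/24: 14.2% |
| Overall, 25 subjects with 9 backfill | 0/16: 20.6% | 0/25: 13.7% |

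**RECIST endpoint**

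The first scheduled scan is after 8 weeks (Section 6.1.4). With two-week cycles and combination from Day 15, combination doses on Days 15, 29 and 43 precede it. The schedule therefore cannot produce a monotherapy response rate.

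**The case against.** The strongest reply is that this is table layout. Section 8 leaves technical detail and table templates to the SAP, and a split by treatment at onset is ordinary SAP content that nothing in Section 8.3.2 forbids. That is fair as far as it goes. However, the protocol does not stay silent: it states a layout for all safety summaries and a denominator for percentages, and a correct monotherapy table would have to depart from the Section 8.1 rule.

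Second, the by-visit layout is informative. Laboratory, vital-sign and ECG summaries at Days 1, 2, 8 and pre-dose Day 15 fall within the monotherapy window. This stands for Cohorts 1-2. In Cohorts 3-5 backfill subjects already on the combination enter the same visits, and no by-visit table gives an adverse-event incidence.

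Third, a reader might infer that the monotherapy limb goes unanswered and that separating events by treatment phase is impossible. The documents do not support that. Onset date and time are recorded (Section 7.2.1), adverse events, SAEs and DLTs are listed (Section 8.3.2), and tolerability after the monotherapy dose is checked before the second and third subjects of a cohort are treated (Section 2.2.1.3). With about three escalation subjects per level, listings carry much of the information.

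Fourth, a reader might take the halved percentage as bias in a planned result. It is not: the plan tabulates no monotherapy percentage. The figures show what the stated denominator would do if it were applied to that window.

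Finally, a phase split cannot deliver clean attribution. The window is 14 days after one dose, and Section 3.1 equates five months with five predicted half-lives, about one month each. Delayed CTL-002 effects will still fall in the combination period. This limit stands and comes from the design. On RECIST, an early End of Treatment scan after monotherapy alone is possible, but it would not give a response rate.

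**Conclusion.** The concern holds for the summaries that the protocol fixes. The Part A primary objective asks for safety as monotherapy and in combination; the adverse-event tables by dose level, overall and visit, over all subjects of the level, give no monotherapy incidence. They mix time windows at every level and, in Cohorts 3-5, also mix in subjects without monotherapy exposure. The possible distortion, 33% to 17% for one event at a level and 21.8% to 14.2% for the overall zero-event upper limit, rests on full backfill and no DLT-driven expansion or replacement. Actual backfill numbers are not given; with none, only the mixing of time remains. The data needed to answer the objective are collected, so this is a correctable mismatch between objective and analysis and not a loss of information.

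Separately, Sections 1.9.2 and 1.10.2 disagree on whether Part A RECIST efficacy includes monotherapy, and the scan schedule can support only the combination.

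**What to change.** - Section 8.3.2: add Part A adverse-event tables by treatment at onset, before versus from the first checkpoint-inhibitor infusion. Use the subjects exposed in that phase as denominator, so that the monotherapy columns contain escalation subjects only, and show backfill subjects separately in the combination period.
- Section 8.1: amend the denominator rule so that phase-specific percentages use subjects exposed in that phase.
- State beside the tables that delayed effects of CTL-002 will appear under the combination.
- Section 1.10.2: remove the monotherapy limb from the Part A RECIST efficacy endpoint so that it agrees with Section 1.9.2.

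The cost is extra table columns built from onset and dosing dates already recorded; no new data are needed. The drawback is small denominators, about 3 per level, so the columns will be imprecise and should be read with the listings.

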8.3.3. Efficacy Analysis

Efficacy analyses will be based on the Efficacy Evaluable Analysis Set and will include summaries of confirmed PR/CR, ORR, DoR, PFS, TTR, and OS by dose level (Part A) or cohort (Part B). Tumor response will be evaluated according to institutional standards using RECIST V1.1 for solid tumors, as well as iRECIST criteria. The definitions of the response evaluation endpoints are as follows:

Table 10 Definitions of Response Evaluation (RECIST V1.1)

Duration of Response:	Duration of response will be measured from the time that measurement criteria are met for CR or PR (whichever status is recorded first) until the first date that PD or death is documented. This analysis will include subjects with overall best response being CR or PR only. Subjects who neither progressed nor died will be censored at the date of the last tumor assessment
Overall Response Rate	Overall response rate is defined as the percentage of subjects with a CR or PR as assessed by RECIST V1.1. A responder is defined as a subject experiencing either a CR or PR by these criteria. Subjects with no tumor assessment after the start of study treatment are to be considered as non-responders.
Progression Free Survival	Progression-free survival is defined as the length of time between first study drug administration and the date of the first occurrence of disease progression or death from any cause.
Time to Response	Time to response will be measured from the time of first study administration until the day of documented CR or PR (whichever status is recorded first). Subjects without response will be censored at the date of the last tumor assessment or the date of death.
Overall Survival	Overall survival is defined as the time from the study drug administration to the date of death, regardless of the cause of death. Subjects who were alive at the time of the analysis will be censored at the date the subject was last known to be alive. Subjects without follow-up assessment will be censored at the day of their last dose and subjects with no post-baseline information will be censored at the time of their first study drug administration.

Abbreviations: CR = complete response; PD = progressive disease; PR = partial response; RECIST = Response Evaluation Criteria in Solid Tumors

For DOR, PFS, TTR and OS, Kaplan-Meier curves and estimates including medians and 95% confidence intervals (CIs) will be provided. For analysis of the ORR, summary tables will be generated, presenting the number and proportion of responders in each dose group and 2-sided 95% Pearson-Clopper CIs. Logistic regression analyses may be used to test potential predictive factors for overall response.

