1.10. Trial Endpoints

1.10.1. Primary Endpoints

Part A (Phase 1; dose escalation):

- Evaluation of the number of subjects with AEs, including serious adverse events (SAEs), clinical laboratory data, vital signs, electrocardiograms (ECGs), physical examination (including neurological assessment) and Eastern Cooperative Oncology Group (ECOG) performance status

Determination of DLTs and maximum tolerated dose (MTD) in Part A of the study using the National Cancer Institute Common Terminology Criteria for Adverse Events (NCI-CTCAE) Version 5.0

Part B (Phase 2a; expansion):

- Evaluation of the clinical efficacy according to Response Evaluation Criteria in Solid Tumors (RECIST) V1.1 of CTL-002 in combination with an anti-PD-1 checkpoint inhibitor by assessment of:
 - The proportion of subjects with tumor shrinkage, a confirmed partial response (PR) and/or complete response (CR), and overall response rate (ORR)
 - The interval between the date of first CTL-002 administration and first documented evidence of a PR or CR (time to response [TTR])
 - The interval between the date of first documented evidence of PR or CR, until first documented evidence of disease progression or death, due to any cause (duration of response [DOR])
 - The interval between the date of first CTL-002 administration and the earliest date of disease progression or death (progression free survival [PFS])
 - The interval between the date of first CTL-002 administration and date of death due to any cause (overall survival [OS])
- Evaluation of the number of subjects with AEs, including SAEs, clinical laboratory data, vital signs, ECGs, physical examination (including neurological assessment), and ECOG performance status

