4.6. Treatment Beyond Progression

The drugs used in this study are meant to induce an immune response against the subject's tumor and may not have an immediate effect on the tumor. In addition, the expected mechanism of action involves an infiltration of T-cells and inflammatory cells and local release of inflammatory cytokines. Therefore, it is expected that initial radiographic progression may not be indicative of subsequent lack of response. Treatment may continue in spite of early radiographic progression,

including appearance of new lesions, in the absence of symptomatic progression as long as the subject has not had an AE that meets the criteria for treatment discontinuation.

Treatment past initial RECIST-defined radiographic progression may continue according to Investigator judgment, in consultation with the Medical Monitor, based on the subject's overall clinical status, overall tumor burden, and rate of progression, taking into account the subject's other treatment options and need for urgent intervention (decisions regarding subject treatment should be made according to site standard of care as determined by the Investigator).

For example, a subject may continue treatment if a tumor assessment shows improvement or stable disease compared to the previous scan, even if there is progression compared to the baseline scan. Investigators may schedule an additional tumor assessment within 8 weeks after a scan showing progression, in order to reassess the subject's response. Subjects may be treated after progression if they meet these criteria:

- Investigator-assessed potential clinical benefit
- No disease-related clinical deterioration
- Absence of progressive tumor at critical anatomical sites (e.g., cord compression) requiring urgent alternative medical intervention
- Subject has not had an AE that meets the criteria for treatment discontinuation

If treatment is continued in spite of radiographic progression, the Investigator should record the rationale, and the subject must be informed that treatment beyond initial progression is not standard of care, and the Investigator should discuss potential risks and alternative treatment options.

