APPENDIX 2. IMMUNE RESPONSE EVALUATION CRITERIA IN SOLID TUMORS (iRECIST)

As defined by modified RECIST V1.1 criteria for immune-based therapeutics or iRECIST criteria ([Seymour et al., 2017](#)), the date of initial potential progression by RECIST scanning will be defined as the iUPD date. Subjects with an iUPD date who are stable will continue to participate in the study as planned and be reassessed for progression 4 to 8 weeks after the initial assessment. If the confirmatory assessment supports PD, the date of disease progression will be the iUPD date. If the confirmatory assessment does not support PD, the subject does not have disease progression and the iUPD date is ignored; such subjects will remain in the study as planned and continue the next imaging evaluation as planned per protocol.

Table 13 Comparison of RECIST V1.1 and iRECIST (Appendix 2)

	RECIST V1.1	iRECIST
Definitions of measurable and nonmeasurable disease; numbers and site of target disease	Measurable lesions are ≥ 10 mm in diameter (≥ 15 mm for nodal lesions) maximum of 5 lesions (2 per organ); all other disease is considered non-target (must be ≥ 10 mm in short axis for nodal disease)	No change from RECIST V1.1; however, new lesions are assessed as per RECIST V1.1 but are recorded separately on the eCRF (but not included in the sum of lesions for target lesions identified at baseline)
CR, PR, or SD	Cannot have met criteria for progression before CR, PR, or SD	Can have had iUPD (one or more instances), but not iCPD, before iCR, iPR, or iSD
Confirmation of CR or PR	Only required for non-randomized trials	As per RECIST V1.1
Confirmation of SD	Not required	As per RECIST V1.1
New lesions	Result in progression; recorded but not measured	Results in iUPD but iCPD is only assigned on the basis of this category if at next assessment additional new lesions appear or an increase in size of new lesions is seen (≥ 5 mm for sum of new lesion target or any increase in new lesion non-target); the appearance of new lesions when none have previously been recorded, can also confirm iCPD
Independent blinded review and central collection of scans	Recommended in some circumstances – e.g., in some trials with progression-based endpoints planned for marketing approval	Collection of scans (but not independent review) recommended for all trials
Confirmation of progression	Not required (unless equivocal)	Required

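### The planned Kaplan-Meier analysis of time to response does not treat death or progression as competing events, so its curve can overstate the cumulative probability of response

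*Protocol*

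**What the plan says.** Table 10 in section 8.3.3 defines the endpoint: "Time to response will be measured from the time of first study administration until the day of documented CR or PR", whichever comes first. On non-responders it says: "Subjects without response will be censored at the date of the last tumor assessment or the date of death". The text after the table fixes the estimator: "For DOR, PFS, TTR and OS, Kaplan-Meier curves and estimates including medians and 95% confidence intervals (CIs) will be provided".

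Table 10 limits duration of response to responders ("This analysis will include subjects with overall best response being CR or PR only"). It sets no such limit for TTR, so every subject in the efficacy analysis set enters the TTR curve. The protocol nowhere treats death or progression as a competing event for response.

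TTR is listed among the Part B primary efficacy endpoints in section 1.10.1 and among the Part A secondary endpoints in section 1.10.2. Both are assessed by RECIST V1.1. On response after progression, Table 13 in Appendix 2 says for RECIST V1.1: "Cannot have met criteria for progression before CR, PR, or SD". For iRECIST it says: "Can have had iUPD (one or more instances), but not iCPD, before iCR, iPR, or iSD".

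**The concern.** Kaplan-Meier assumes that a censored subject would go on to have the event at the same rate as those still under observation. That is reasonable for someone whose follow-up is merely incomplete. It fails for a subject who has died, and for one who has met RECIST V1.1 progression, because neither can have the event any more. Censoring them removes them from the denominator, and each later response then counts for more than its share.

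The same section also reports ORR as a plain proportion, with non-responders kept in the denominator. One report could therefore show two different answers on the probability of response from the same subjects. The design response rates are 20% to 30% in relapsed or refractory disease, so most subjects are expected to leave without responding. That is the setting in which the distortion can be largest.

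**Working it through.** The protocol gives no TTR figure to reproduce. The check compares the planned estimator with the cumulative incidence of response. The protocol supplies the 8-weekly scans, the 20% design response rate and the 4/27 expansion threshold (section 8.1). Drop-out rates and response timing are assumptions, because the protocol gives none.

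**Formulas.** 1-KM = 1 − Π(1 − dⱼ/nⱼ), where dⱼ is the number of responses at scan j and nⱼ the number still at risk. With every subject's outcome known, the cumulative incidence is responders to date divided by all subjects.

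**Small cohort, 4 responders of 27.** Responses 2/1/1 at weeks 8/16/24.
- Non-responders leave 13/5/2/3 at weeks 8/16/24/32. At risk: 27, 12, 6. Survival function = 25/27 × 11/12 × 5/6 = 0.707, so 1-KM = 29.3%, against 4/27 = 14.8%.
- Slower drop-out, 10/6/3/4. At risk: 27, 15, 8. 25/27 × 14/15 × 7/8 = 0.756, so 1-KM = 24.4%, against 14.8%.
- All four responses at week 8: 1 − 23/27 = 14.8% by both methods, so no bias.

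**Larger illustration, per 100 subjects.** Twenty responders, with shares 50/30/15/5% at weeks 8/16/24/32, give 10, 6, 3 and 1 responses. Eighty non-responders leave with a median of 2.5 months. Eight weeks is about 1.84 months, so the fraction retained per interval is 0.5^(1.84/2.5) = 0.60. Taking the last scan as the point of leaving:

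| Week | At risk | Responses | 1-KM | True incidence |
|---|---|---|---|---|
| 8 | 20 + 80 = 100 | 10 | 10.0% | 10% |
| 16 | 10 + 48 = 58 | 6 | 19.3% | 16% |
| 24 | 4 + 28.8 = 32.8 | 3 | 26.7% | 19% |
| 32 | 1 + 17.28 = 18.28 | 1 | 30.7% | 20% |

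**Scans after progression.** Table 10 censors at the last scan, not at progression, so further scans keep a progressed subject in the denominator for longer. Week-32 results in the same scenario:
- Half of the non-responders have one further 8-weekly scan: 90/100 × 68/74 × 39.4/42.4 × 23.04/24.04 = 0.737, so 26.3%.
- All have one further scan: 90/100 × 84/90 × 49/52 × 28.8/29.8 = 0.765, so 23.5%.
- All have two: 90/100 × 84/90 × 81/84 × 48/49 = 0.793, so 20.7%.

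**Earlier responses.** With 80% of responses at week 8, 20% at week 16 and no extra scans: 84/100 × 48/52 = 0.775, so 22.5% against 20%.

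**The case against.** The strongest reply is that the rule does not censor at progression, and that the protocol provides for imaging afterwards. Section 4.6 says: "Treatment past initial RECIST-defined radiographic progression may continue according to Investigator judgment", and allows an additional scan within 8 weeks. Section 6.2.5.1 has stable subjects with unconfirmed progression rescanned after 4 to 8 weeks, and section 6.1.11 continues imaging by local practice in follow-up. This stands. It can bring the illustration down from 31% towards 21%. It does not remove the fault, because subjects who die or stop imaging get no further scan.

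A reader might go further and infer that the TTR curve and median are biased or undefined in every cohort. The documents do not support that. The bias is zero when no progression or death precedes the last response, and small when responses come early. A median that is not reached is ordinary Kaplan-Meier output; in the larger illustration the curve ends at 31%, so no spurious median is produced.

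A reader might also infer that the reported response rate, or the choice of cohorts to expand, is inflated. It is not. ORR is a separate proportion with an exact interval, and Table 10 counts subjects with no tumor assessment after treatment start as non-responders. The Simon expansion rules use responder counts. Section 8.1 describes the study as exploratory with no formal comparisons, and no threshold is attached to TTR.

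Finally, under exploratory iRECIST an unconfirmed progression does not rule out a later response. There, only death and confirmed progression end the possibility.

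**Conclusion.** The concern holds. The protocol itself fixes both the censoring rule and the estimator. Under RECIST V1.1, 1-KM from this analysis is not a valid cumulative probability of response once death or progression precedes later responses. In the larger illustration (true rate 20%), the week-32 value is about 21% to 31% depending on scans after progression. In the two 4/27 examples with later responses it is 24% to 29% against 15%. These sizes rest on assumed drop-out and response timing and are not predictions. The effect is confined to the TTR curve, its median and its interval. It deserves correction because TTR is listed among the Part B primary endpoints and the remedy is simple.

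**What to change.** In section 8.3.3, remove TTR from the list of endpoints analysed by Kaplan-Meier, and delete the TTR censoring sentence from Table 10. Make the matching change in the synopsis. Summarise TTR as median and range among responders, using the same responder definition as the ORR analysis so that the two tables describe the same subjects.

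If a curve over all subjects is wanted, use the Aalen-Johansen cumulative incidence of response. The competing event is death or RECIST V1.1 progression without prior response; for an iRECIST version it is death or confirmed progression.

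The cost is a short text change and a standard procedure, with no new data. The downside is that a responders-only summary will describe few subjects in each cohort.
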